Cerebral microdialysis is a well-established laboratory tool that is increasingly used as a bedside monitor of brain tissue biochemistry in the neurocritical care unit. Metabolic crisis, measured in the interstitial space by cerebral microdialysis, is defined as a high lactate pyruvate ratio (LPR >40) in combination with a low extracellular cerebral glucose level (<0.7 mmol/l).⁷⁷⁻⁷⁹ Serum glucose levels directly affect the availability of extracellular brain glucose and therefore brain metabolism. Under optimal conditions, energy supply to the brain is adjusted to meet the individual demand, which is higher after severe brain injury.⁸⁰⁻⁸¹ A reduction in energy supply can be caused by reduced cerebral blood flow, which decreases oxygen and glucose supply, resulting in a shift to anaerobic metabolism with increased brain lactate.⁸² Alternatively, low glucose availability can lead to a decrease in brain pyruvate without an increase in lactate.^{32,72} This metabolic crisis has been linked to poor outcome in comatose patients.^{83,84}

Recently, tight glycemic control with IIT has been associated with metabolic crisis in patients with acute brain injury.^{32,49,71} In these studies, tight glucose control (goal 80-120 mg/dL) was associated with a significant increase in the incidence of dialysate glucose levels <0.7 mmol/L, LPR >30, and increased in glutamate. Marcoux et al. reported that the percentage of time LPR was above 30 was significantly correlated with the extent of frontal lobe atrophy 6 months following injury even in patients with a normal frontal lobe on initial CT scan.⁵⁰ It is becoming apparent that IIT is not only associated with hypoglycemic episodes but also with direct extracellular evidence of cellular distress and brain metabolic crisis.

Therefore, in neurocritical care patients, interventions that maintain cerebral extracellular glucose levels without causing an increase in markers of cellular distress are anticipated to be particularly effective in the management of acute hyperglycemia. We propose to determine the impact of exenatide infusion on cerebral extracellular glucose levels in eligible critically ill patients with acute brain injury.

APPROACH

Study Design: Single-center, prospective, non-randomized, open-label feasibility demonstration trial of exenatide infusion following acute brain injury.

Randomized Design (if applicable): NA

Study Population: Critically ill patients with acute brain injury.

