1. Subjects: Adult patients (≥ 18 years) with two consecutive blood glucose readings of > 150 mg/dL and ≤ 300 mg/dL will be eligible for inclusion in this study. The study population will be limited to those with acute brain injury resulting in admission to the NSICU for an anticipated length of stay >48 hours and who will not have planned steroid use post-operatively. Patients with imminent brain death or refractory intracranial hypertension will not be enrolled. Pregnant (verified by urine or serum pregnancy test within 24 hours of initiation of exenatide infusion) or lactating females, and those with a history of type 1 diabetes mellitus, pancreatitis or risk factors for acute pancreatitis (i.e. ethanol abuse, gall stones), renal insufficiency (CrCL < 45 mL/min), gastroparesis, surgery on stomach, esophageous, or duodenum or those with organ transplantation will be excluded. Additionally, those presenting with diabetic ketoacidosis or hyperosmolar hyperglycemic nonketotic syndrome will be excluded. Individuals receiving steroids or planned post-operative administration, insulin infusion within 3 hours of study drug administration, long acting insulin or sulfonylureas within 24 hours of study drug administration, another investigational drug or device, or those with known allergy to any of the study protocol drugs will be excluded. Recruitment will continue until 24 subjects receive study drug and complete the study protocol.

2. Glycemic Control Protocol: All study related protocols will be conducted in the Neuroscience Intensive Care Unit (NSICU). All patients admitted to the NSICU and that meet the eligibility criteria will be approached for consent to the study. Study drug will only be administered to those subjects providing consent via legally authorized representative and meeting glycemic thresholds. The study nurse will initiate the exenatide infusion

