2 DATA MONITORING COMMITTEE AND OTHER EXTERNAL COMMITTEES

Not applicable

8. Measurements: Blood glucose from the arterial line will be measured at baseline (prior to exenatide), hourly during the 48 hour exenatide infusion per protocol (table 2) and continue for an additional 24 hours following exenatide discontinuation. The continuous glucose monitor will measure the interstitial glucose level every 5 minutes beginning at baseline (prior to exenatide) until 24 hours following exenatide discontinuation. Blood samples for pharmacokinetic analysis will be collected in serum separator tubes at 0, 12, 24, 36 and 48 hours after the start of the infusion. Eight-hour urine collections will be obtained on a daily basis for 72 hours (48 hours during study drug infusion and an additional 24 hours during follow-up after study drug is discontinued). Microdialystate concentrations will be collected at baseline (prior to exenatide), and hourly during the 48-hour exenatide infusion for parameters of energy metabolism (glucose, pyruvate, lactate, lactate:pyruvate ratio), glutamate (marker of cerebral ischemia), and glycerol (marker of cell membrane degradation) and for an additional 24 hours following study drug discontinuation. Blood pressure will be measured continuously throughout the study period. Intracranial pressure (ICP) will be measured continuously during the exenatide infusion. Intracranial pressure values will be recorded at baseline (prior to exenatide) and daily mean ICP and cerebral perfusion pressure values will be reported. Baseline demographic information (e.g. gender, age, ethnicity) and disease severity information [e.g. Glasgow coma score, SOFA score (Sequential Organ Failure Assessment), Hunt Hess classification, Fisher grade, primary diagnosis, past medical history (including measurement of hemoglobin A1c), neurologic exam/computed tomography scan abnormalities] will be collected. The ICU day of study drug administration will be recorded and the total hospital and ICU lengths of stay will be recorded.

9. Data Management: Each participant will be assigned a unique identification number. No personal identification will be used. All study files will be stored in locked cabinets in the Principal Investigator's office in the Pharmacy Administration Department. Data will be entered into the study database using double entry (entry and verification) and will be checked for missing or ineligible responses.

10. Outcomes

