10.1 The following feasibility endpoints are based upon prior literature (Nice-Sugar and Exenatide Study in the Cardiac ICU):

Proportion of patients experiencing severe hypoglycemia (<40 mg/dL), Proportion of patients achieving plasma glucose goal (110-180 mg/dL), Proportion of patients experiencing nausea requiring discontinuation of exenatide therapy

10.2 The following descriptive endpoints are included for describing experience with exenatide use in the NSICU population:

Average blood glucose value during exenatide infusion (48 hours), percent time in glucose range (48 hours), mean time to reach plasma glucose goal (110-180 mg/dL), variability outcome (SD)-MADGE, mean insulin use required (units/kg body weight), proportion of subjects requiring rescue insulin infusion protocol, number of hypoglycemic episodes (<80 mg/dL)/total number of glucose measurements (48 hours), number of subjects with >1 hypoglycemic episode (<80 mg/dL)/total number of subjects (48 hours), correlation of exenatide concentrations with creatinine clearance during infusion, elimination rate constant and area under the concentration-time curve utilizing concentrations after discontinuation of infusion, side effects and adverse events (AEs and SAEs), average daily ICP and CPP during study drug infusion, number of hypotensive episodes (SBP<100 mmHg) (48 hours), number of subjects with >1 hypotensive episode/total number of subjects (48 hours). Other adverse effects will be collected specifically assessing any alterations in gastric motility.

In patients receiving invasive intracranial multimodal monitoring as part of their standard of care, the following endpoints associated with exenatide use will be described:

Percent time outside of range for energy metabolism (glucose <0.7 mmol/L and lactate:pyruvate ratio > 40), glutamate (marker of cerebral ischemia), and glycerol (marker of cell membrane degradation) parameters (48 hours).

Based upon prior literature, the prespecified criteria for determining feasibility include the following: 1) no more than 6 patients (25%) experiencing severe hypoglycemia (<40 mg/dL); 2) at least 18 patients (75%) achieving the plasma glucose goal (110-180 mg/dL); 3) no more than 6 patients (25%) experiencing nausea leading to exenatide discontinuation. These criteria will be utilized to determine whether a future efficacy trial will be pursued.

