11. Sample size and justification: A sample size was determined using prior exenatide in critically ill patients studies and patient screening information at our site. Based upon this data, we determined to enroll 24 patients who complete 48 hours of exenatide infusion and continuous glucose monitoring. In eligible patients, cerebral microdialysis monitoring will also be performed. It is estimated based on proposed eligibility criteria that 24% (n = 200) patients admitted to the NSICU will be eligible for enrollment annually. With an approximate rate of enrollment at 15 – 20%, we are confident we could enroll 30 – 40 subjects annually.

12. Data analysis plan: Prior to analysis, data will be examined for errors, outliers, and asymmetry. When appropriate, transformations will be used to reduce asymmetry. An intent-to-treat analysis (defined as all individuals consented in the study) will be utilized. Descriptive statistics will be performed. Data will be expressed as means \pm standard error (SE) or success rates and corresponding 95%CI for continuous and

dichotomous outcomes, respectively. Analyses will be completed using the statistical software package SAS, version 9.2 (SAS institute, Cary, North Carolina).

13. Ethical consideration: The consent procedures will be reviewed and approved by the Institutional Review Board. All subjects will provide written informed consent via proxy. The informed consent process will allow the proxy to gain an in-depth knowledge of the study purposes and procedures and allow them to make informed decisions about willingness to proceed. Participation is voluntary. The proxy will be encouraged to ask questions and will be assessed for adequate understanding.

Exenatide required: yes

Placebo required: no

Clinical study duration of treatment: Subjects will be exposed to exenatide treatment for 48 hours.

Clinical study dosing schedule and frequency: exenatide 50 ng/min for 30 minutes, start exenatide infusion 25 ng/min x 48 hours

Clinical study number of sites: one

Clinical study expected number of subjects screened: It is estimated based on proposed eligibility criteria that 24% (n = 200) patients admitted to the NSICU will be eligible for enrollment annually with an approximate rate of enrollment at 15-20%.

Clinical study expected number of subjects enrolled: 24

Clinical study expected number of subjects to complete study: 24

Planned Study Start Date: January 1, 2015

Planned Study End Date: June 30, 2016

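### Enrolment is not linked to the trial's own feasibility limits: read as counts of treated patients, a 7th hypoglycemia or nausea event settles the answer, but recruitment goes on

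*Combined protocol and SAP*

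**What the plan says.** The Approach section describes a "Single-center, prospective, non-randomized, open-label feasibility demonstration trial of exenatide infusion following acute brain injury". Methodology item 1 states that "Recruitment will continue until 24 subjects receive study drug and complete the study protocol", and item 11 repeats the target: "we determined to enroll 24 patients who complete 48 hours of exenatide infusion and continuous glucose monitoring".

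The feasibility criteria close Outcomes 10.2: "no more than 6 patients (25%) experiencing severe hypoglycemia (<40 mg/dL"), "at least 18 patients (75%) achieving the plasma glucose goal (110-180 mg/dL") and "no more than 6 patients (25%) experiencing nausea leading to exenatide discontinuation". Their only stated use is for what comes next: "These criteria will be utilized to determine whether a future efficacy trial will be pursued".

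Under Safety Data, section 2, headed "DATA MONITORING COMMITTEE AND OTHER EXTERNAL COMMITTEES", is marked not applicable. Item 12 plans descriptive statistics on everyone who consented, with no interim look. The safeguards that do exist are glucose-driven infusion rules for the individual patient (item 2, Tables 1 and 2), physician contact for low blood pressure, and reporting of serious adverse events within 24 hours (section 1.1.1). None of them acts on enrolment.

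**The concern.** Two of the three criteria are upper limits on a number of patients. Once such a limit is passed it cannot be undone by later patients, provided it is a count. From then on the go/no-go answer is negative, yet the recruitment rule would still bring in new patients, by proxy consent, until 24 have completed.

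Replacement adds to this. The 24 must complete 48 hours of infusion, so a patient who stops for nausea seems to be a non-completer whose place is filled. The more often the drug is stopped for nausea, the more patients are treated.

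What is at stake is exposure that no longer serves the feasibility decision, in a population for which the protocol's own background links low glucose to worse outcome. The trial is open-label at one site, so the information needed to notice this is already in the team's hands.

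**Working it through.** **The plan's own figures.** 6/24 = 25% and 18/24 = 75%, so the counts and percentages in 10.2 agree exactly at 24 patients. The sample size of 24 cannot be reproduced, because item 11 gives no error rate, power or expected event rate.

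**Inputs.** Limit of 6 for hypoglycemia and for nausea discontinuation (10.2); 24 patients (items 1 and 11). The true rate *p* is not in the documents and is an assumption, shown from 10% to 50%.

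**Case A: exactly 24 treated, limits read as counts.** Let T be the patient in whom the 7th event occurs. Then

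P(T = t) = C(t−1, 6) p⁷ (1−p)^(t−7), for t = 7 to 24.

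P(limit exceeded) is the sum over t, equal to P(Binomial(24, p) ≥ 7). Mean number treated with closure at the 7th event = 24 − Σ (24 − t) P(T = t). Mean treated after the 7th event, given that it occurs = Σ (24 − t) P(T = t) / P(limit exceeded).

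| True rate | P(7th event within 24) | Mean treated with closure | Mean treated after 7th event, if it occurs |
|---|---|---|---|
| 10% | 0.7% | 23.98 | 2.8 |
| 20% | 19% | 23.3 | 3.8 |
| 25% | 39% | 22.2 | 4.5 |
| 35% | 79% | 18.9 | 6.4 |
| 50% | 99% | 14.0 | 10.1 |

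The earliest the limit can be exceeded is patient 7, leaving at most 24 − 7 = 17 still to treat. The table applies to each of the two limits separately.

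**Case B: every nausea stop is replaced (assumption).** With stop rate *q* and no other reason for non-completion, the mean number treated to reach 24 completers is 24/(1 − q). With closure at the 7th stop it is

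Σ(c = 0..23) (c+7) C(c+6, 6) q⁷ (1−q)^c + Σ(s = 0..6) (24+s) C(23+s, s) q^s (1−q)²⁴.

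| Stop rate | Mean treated, no closure | Mean treated, closure at 7th stop | P(7th stop before 24th completer) |
|---|---|---|---|
| 20% | 24/0.80 = 30 | 26.6 | 39% |
| 25% | 24/0.75 = 32 | 24.7 | 65% |
| 30% | 24/0.70 = 34 | 22.2 | 84% |

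**Dependence on the denominator.** If 25% is applied to a larger set, the 7th event is not final: 7/28 = 25.0%, 7/30 = 23.3%, 7/34 = 20.6%, all within the limit. Item 12's analysis set is everyone consented, which is not the same set as the 24 completers.

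**Glucose-goal criterion.** With exactly 24 patients, a 7th failure leaves at most 17 successes and the criterion fails. If more than 24 are treated, 18 successes can still be reached, so its failure is final only with a fixed denominator.

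**Practicality.** Item 11 expects 200 × 15% = 30 to 200 × 20% = 40 patients a year, or one about every 365/40 = 9 to 365/30 = 12 days, against 72 hours of observation per patient. A count updated after each patient is workable.

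**The case against.** A reader might infer that the trial is bound to go on after a criterion has failed for certain, whatever the reading. The documents do not support that. Each limit is given as a count and as a percentage, and the percentage reading leaves a 7th event open once more than 24 are in the denominator. On that reading, closing at the 7th event could itself change the decision: at a true rate of 20%, a trial that would finish above 6 events but within 25% has probability 15% with 30 treated (exactly 7 events) and 31% with 34 treated (7 or 8 events). This objection stands, and it is why the denominator must be settled before any closure rule is written.

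The background also points towards low rates: no symptomatic hypoglycemia with subcutaneous exenatide in stroke, few gastrointestinal effects with infusion, and hypoglycemia absent from most GLP-1 infusion studies. The high nausea rate quoted there (55%) is for subcutaneous use and is not a rate of discontinuation. At 10% or below the closure rule would almost never act. That stands too. It limits the expected benefit, but it also means the rule costs almost nothing when the drug performs well.

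It is also tempting to say that later patients contribute nothing, or that exposure is unlimited. Neither follows. The pharmacokinetic and microdialysis aims do not depend on the feasibility criteria, so later patients still inform them. The closing summary after item 13 expects 24 enrolled and 24 completing, with a planned end date. What is missing is a stated cap on replacement.

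Finally, a rule that acts only at a 7th event is mainly a futility rule and adds little safety. Patient-level infusion rules and serious-event reporting already exist, so it would be wrong to say that there is no oversight.

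**Conclusion.** The point holds in a conditional form. No trial-level check ties enrolment to the feasibility limits. If the hypoglycemia and nausea limits are counts among treated patients, enrolment can continue after the go/no-go answer is already negative.

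The size depends wholly on unknown rates. With 24 treated, the mean saving is 0.02 patients at 10%, 0.7 at 20%, 1.8 at 25%, 5.1 at 35% and 10.0 at 50%. If every nausea stop is replaced, the mean saving is 30 − 26.6 = 3.4 patients at a 20% stop rate and about 12 at 30% (34.3 − 22.2).

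These figures assume independent patients with a common event rate, the count reading, and that each criterion must be met. On that reading, closure leaves the go/no-go decision unchanged. It is an improvement worth considering rather than a required correction.

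**What to change.** 1. In Outcomes 10.2, state that the hypoglycemia and nausea limits are counts among all treated patients. Reconcile this with the 24 completers in items 1 and 11 and with the all-consented analysis set in item 12, and say whether non-completers are replaced and up to what total.

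2. Then add to Methodology item 1 and to item 11 that the study team keeps a running tally, and that once either of the protocol's own limits is exceeded, enrolment closes and the trial is reported as not meeting feasibility. The tally should draw on the hourly glucose record and on the adverse event forms. Serious-event reporting alone is not enough, since a nausea discontinuation would ordinarily be recorded as nonserious (section 1.2.1).

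3. Leave the glucose-goal criterion out of the closure rule unless its denominator is fixed.

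This uses the sponsor's existing limits, introduces no new clinical threshold, and needs no committee. The cost is a few sentences and a tally. The downside is fewer patients for the pharmacokinetic, microdialysis and descriptive aims, but only in a trial that has already failed a criterion.

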for the second consecutive blood glucose value >150 mg/dL but ≤ 300 mg/dL and continue per protocol for a maximum duration of 48 hours. Exenatide will be administered by intravenous infusion (50 ng/min for 30 minutes, then start exenatide infusion 25 ng/min) for the second consecutive blood glucose value >150 mg/dL but ≤ 300 mg/dL and continue per protocol for a maximum duration of 48 hours (dose, route, titration schedule, and duration). Exenatide will be prepared by the Investigational Drug Service. The exenatide infusion initiation and maintenance protocols are outlined in Tables 1&2 of the attached study protocol. The exenatide infusion blood glucose goal will be 110-180 mg/dL. During the exenatide infusion, glucose measurements will be obtained hourly. The exenatide infusion will be temporarily discontinued for blood glucose <110 mg/dL. The exenatide infusion will be restarted once the blood glucose level is at least 110 mg/dL. Episodes of hypoglycemia will be treated according to the following guidelines: 1) glucose <70 mg/dL will be provided 25 mL of dextrose 50% (1/2 amp) 2) blood glucose will be re-checked in 5 minutes; if mental status changes caused by hypoglycemia are not reversed or blood glucose remains <70 mg/dL, the above dextrose administration will be repeated, 3) serum glucose will be checked hourly after dextrose administration and the episode has resolved. Exenatide infusion will be restarted beginning with the second hourly glucose check that is ≥ 110 mg/dL. Insulin sensitive sliding scale using formulary rapid acting insulin will be used for blood glucose 181-300 mg/dL starting at the 2nd hourly glucose check (≥ 2 hours since exenatide initiation). The physician will be notified for any blood glucose >300 mg/dL for initiation of a rescue insulin infusion protocol. All glucose values will be documented in the ICU Electronic Documentation System.

Table 1: Exenatide Infusion Initiation Protocol

Glucose (mg/dL)	Action
151-300	
Give exenatide 50 ng/min for 30 minutes, then start exenatide infusion 25 ng/min
 
Give prokinetic agent per NSICU protocol (reglan, erythromycin, etc)
 
Check glucose hourly
 
Monitor blood pressure continuously during exenatide infusion. If SBP <100 mmHg, contact physician. Decision to discontinue exenatide infusion will be made at the discretion of the treating physician.

Table 2: Exenatide Infusion Maintenance Protocol

Glucose (mg/dL)	Action

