<70	
Discontinue exenatide infusion.
 
Give 25 mL of dextrose 50% (1/2 amp) IVP – Recheck glucose in 5 minutes and notify physician.
 
Check glucose hourly after hypoglycemia is resolved.
 
When 2 in a row hourly glucose checks are greater than 109 restart exenatide infusion at 25 ng/min
 
Notify physician when glucose greater than 80 mg/dL
 
Monitor blood pressure continuously during infusion (if SBP <100 mmHg, contact physician)

80-109	
Temporarily discontinue exenatide infusion
 
Check glucose hourly
 
When glucose greater than 109 restart exenatide infusion at 25 ng/min
 
Note: If 3 in a row hourly checks are less than 110 restart protocol from beginning. Change glucose check to q4h and exenatide protocol for second glucose greater than 180 mg/dL
 
Monitor blood pressure continuously during infusion (if SBP <100 mmHg, contact physician)

110-180	Continue exenatide infusion per protocol Check glucose hourly Monitor blood pressure continuously during infusion (if SBP<100 mmHg, contact physician)
181-216	1 st hourly glucose check (=1 hour since exenatide initiation): continue exenatide infusion protocol ≥2 nd hourly glucose check (≥2 hours since exenatide initiation): Give 2 units of formulary available rapid acting insulin subcutaneously and continue exenatide infusion protocol Check glucose hourly Monitor blood pressure continuously during infusion (if SBP <100 mmHg, contact physician)
217-252	1 st hourly glucose check (=1 hour since exenatide initiation): continue exenatide infusion protocol ≥2 nd hourly glucose check (≥2 hours since exenatide initiation): Give 4 units of formulary available rapid acting insulin subcutaneously and continue exenatide infusion protocol Check glucose hourly Monitor blood pressure continuously during infusion (if SBP <100 mmHg, contact physician)
253-300	1 st hourly glucose check (=1 hour since exenatide initiation): continue exenatide infusion protocol ≥2 nd hourly glucose check (≥2 hours since exenatide initiation): Give 6 units of formulary available rapid acting insulin subcutaneously and continue exenatide infusion protocol Check glucose hourly Monitor blood pressure continuously during infusion (if SBP <100 mmHg, contact physician)
>300	Recheck blood glucose within 5 minutes If confirmed, contact physician to discontinue exenatide and initiate rescue insulin infusion protocol (NSICU insulin infusion protocol)

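### After a glucose below 70 mg/dL, the protocol gives no single consistent rule for resuming exenatide and does not say which line governs during recovery

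*Combined protocol and SAP*

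**What the plan says.** Four places in the protocol bear on restarting the infusion after a low reading.

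- **Table 2, <70 row.** The infusion is stopped, dextrose is given and glucose is checked hourly once the episode resolves. Then: "When 2 in a row hourly glucose checks are greater than 109 restart exenatide infusion at 25 ng/min".
- **Methodology item 2 (Glycemic Control Protocol), hypoglycemia guidelines.** After the treatment steps for a value below 70: "Exenatide infusion will be restarted beginning with the second hourly glucose check that is ≥ 110 mg/dL".
- **Methodology item 2, general hold rule, just before those guidelines.** "The exenatide infusion will be temporarily discontinued for blood glucose <110 mg/dL". The next sentence reads: "The exenatide infusion will be restarted once the blood glucose level is at least 110 mg/dL".
- **Table 2, 80-109 row.** "When glucose greater than 109 restart exenatide infusion at 25 ng/min". The row adds: "Note: If 3 in a row hourly checks are less than 110 restart protocol from beginning". It continues: "Change glucose check to q4h and exenatide protocol for second glucose greater than 180 mg/dL".

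No sentence ranks these lines or says which Table 2 row applies once a patient treated for a value below 70 has risen into 80-109.

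**The concern.** The two lines written for a value below 70 differ in one respect: the table requires the qualifying checks to be adjacent and the narrative does not. The omission is not obviously loose drafting, because the eligibility and initiation text in Methodology items 1 and 2 does say consecutive where two readings must be adjacent.

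The general hold rule is a second source of conflict. A value below 70 is also below 110, so its one-check restart literally applies. The 80-109 row raises a third question, since a recovering patient may pass through that range and the row has its own restart rule and its own three-check note.

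At stake is consistent delivery of a safety-relevant instruction. Two nurses holding the same readings could restart study drug at different hours. The trial also reports outcomes downstream of re-exposure (Outcomes 10.1 and 10.2): severe hypoglycemia below 40 mg/dL, subjects with more than one episode below 80 mg/dL, and percent time in range.

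**Working it through.** The plan states no figure that depends on this rule, so there is none to reproduce. The check applies each line, as worded, to the same readings.

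**Step 1: threshold.** For whole-number readings, above 109 and at least 110 are the same condition. The lines differ in how many qualifying checks are needed and whether they must be adjacent, not in level.

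**Step 2: all three-check patterns.** Let H be an hourly check of 110 or more and L one below 110, counted after the episode resolves. There are 2 × 2 × 2 = 8 patterns. Entries are the check at which the infusion first resumes; a dash means not by check 3.

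| Pattern | Table 2 <70 row (two adjacent H) | Hypoglycemia text (second H, cumulative) | General sentence (first H) |
|---|---|---|---|
| HHH | 2 | 2 | 1 |
| HHL | 2 | 2 | 1 |
| HLH | – | 3 | 1 |
| HLL | – | – | 1 |
| LHH | 3 | 3 | 2 |
| LHL | – | – | 2 |
| LLH | – | – | 3 |
| LLL | – | – | – |

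The two <70-specific lines differ in HLH only, 1 of 8. The general sentence differs from the <70 row in 7 of 8, all but LLL.

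**Step 3: four checks.** Over the 16 four-check patterns, the two <70-specific lines differ in 4 (HLHH, HLHL, HLLH, LHLH). The general sentence differs from the <70 row in 15. If the hypoglycemia text is read as any qualifying value from the second hourly check onward, it differs from the <70 row in 10.

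**Step 4: hours, on assumed readings (mg/dL) after a value below 70.**

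| Readings | <70 row | Hypoglycemia text (cumulative) | 80-109 row, if it takes over | General sentence |
|---|---|---|---|---|
| 115, 118, 120, 125 | 2 | 2 | not entered | 1 |
| 95, 115, 118, 120 | 3 | 3 | 2 | 2 |
| 115, 100, 112, 118 | 4 | 3 | 3 | 1 |
| 95, 100, 105, 115, 120 | 5 | 5 | 4 | 4 |

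In the last sequence the three-check note is met at hour 3. If it applies, checks become four-hourly and re-entry waits for a second value above 180, so the table's hours 4 and 5 no longer hold.

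The readings are illustrations and the pattern counts are not probabilities. The documents give nothing with which to weight them.

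**The case against.** The strongest reply is that the plan can be read coherently. The hypoglycemia sentence is more specific than the general hold rule and follows it, so it would normally prevail. The two <70-specific lines share a threshold and a number of checks, and on the cumulative reading they agree unless glucose dips between qualifying checks. All readings require at least 110 mg/dL before restart. The trial has a single arm, so no between-group bias arises.

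These points narrow the problem but do not remove it. The specific-over-general reading is an inference, since the plan states no precedence, and the difference over adjacent checks remains even if it is accepted.

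A reader might go further and infer three competing rules for the same event, with disagreement in 4 of 8 three-check patterns (HLH, LHH, LHL and LLH). The documents do not support that. It requires the 80-109 row to take over from the <70 row during recovery, which no text says, and the structure points the other way:

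- The 80-109 row opens by pausing an infusion, whereas after a value below 70 it is already off.
- The <70 row still gives an instruction once glucose has passed 80.
- If Table 2 followed current glucose alone, a patient recovering straight to 115 would fall in the 110-180 row, and the two-check rule of the <70 row could not operate.
- LLH is doubtful even on that premise. If the value below 70 was itself an hourly check, it and the two L readings already make three in a row below 110, and the note would apply first.

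What stands is that the governing row is unstated, not that the 80-109 row supplies a third rule for this event.

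**Conclusion.** The inconsistency is real and narrow. The two lines specific to a value below 70 conflict over whether checks must be adjacent, which matters in 1 of 8 three-check patterns. The general sentence, read literally, conflicts with both, and the row that governs a recovering patient at 80-109 is not stated. In the illustrations restart differs by one to three hours (hour 4 against hour 1 at most). This rests on hourly checks, whole-number readings and each line applied as worded, and it concerns only patients who have a value below 70.

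A reader might infer that the feasibility decision is compromised, in particular the limit of 6 of 24 patients (25%) with glucose below 40 mg/dL. The documents do not show this. They give no rate of values below 70 and no link from restart timing to a later severe episode, so neither the size nor the direction of any effect is known. Nor should the hypoglycemia text be taken to require a second reading at goal: it sets no upper limit, whereas "The exenatide infusion blood glucose goal will be 110-180 mg/dL". The sample size and all other statistical figures are unaffected. The point is worth acting on because the instruction bears on safety and clarifying it costs almost nothing.

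**What to change.** The investigators should reconcile both restart sentences in Methodology item 2 with the <70 and 80-109 rows of Table 2, so that they give one instruction for resuming exenatide after a value below 70 mg/dL. It should state whether the qualifying checks must be consecutive, which line governs while a recovering patient reads 80-109, and whether the three-check note applies to that patient. Which rule to adopt is a clinical decision for the investigators.

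Optionally, record the time of each pause and resumption. Glucose values are already documented and medications during the infusion recorded, but nothing explicitly asks for these times. With them, re-exposure after hypoglycemia could be reported.

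The cost is a wording change in two places. The optional item adds two time fields per interruption and no procedure for the patient.
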